# Abbreviations and acronyms

# 1.Introduction

The Global technical strategy for malaria 2016-2030, approved by the World Health Assembly in May 2015, set ambitious but achievable targets for 2030, including a reduction of at least 90% in global malaria incidence and mortality (WHO, 2015a). The World Health Organization (WHO) recommended malaria interventions namely quality assured vector control, chemoprevention. diagnosing and treatment of the interventions recommends implementing to attain the intended target (WHO, 2015c). In sub-Saharan Africa, the recommended malaria interventions namely Long Last Insecticide treated Nets (LLINs) delivered by manufacturers have increased in recent years, rising from 5.6 million in 2004 to 145 million in 2010. Nearly 300 million LLINs were delivered to African countries between 2008 and the end of 2010. Meanwhile, the number of people protected by Indoor Residual Spray (IRS) in the WHO African Region increased from 10 million to 78 million in 2010. Globally by 2005, 185 million people were protected by IRS and by 2010, representing 6% of the global population at risk were protected by the same intervention. In 2013, 124 million people were protected by IRS, representing 4% of the global population at risk (WHO 2015b).

On previous literature IRS and LLINs can build its acceptability in a community by its killing and knock down effect of insects but recent studies indicate that target vector populations are developing resistance to the chemicals used in IRS and LLINs. Consequently, malaria intervention tools are considered not as effective and trusted in these intervention methods as a malaria protective tool. These newly observed challenge may be an obstacle in attaining the strategic goal set by WHO (Baume C. et. al., 2007).

Use of LLINs substantially reduces malaria mortality and morbidity. Currently manufacturers have developed treatment processes, in which the insecticide is more stably bound to fabrics that are more wash resistant, resulting in long-lasting. The introduction of these LLINs, ideally lasting the entire lifetime of a mosquito net, is considered a possible solution to this problem. With the support of the World Health Organization (WHO) the use of LLINs in the vector control strategy was adopted in Ethiopia during 1997/98 with the intention of gradual scaling up. Following this the National Malaria Control Programme has distributed.

LLINs and curtains have repeatedly been shown to reduce malaria morbidity and mortality in sub-Saharan Africa (Lengeler, 2004). Wide use of LLINs was shown to reduce incidence and provide significant protection in children against overall mortality, mortality attributed to malaria, clinical attacks of malaria and malaria infection (Alonso et al., 1993; D'Alessandro et al., 1995; Maxwell et al., 1999). Guidelines for testing long-lasting insecticidal nets (LNs) were first published by WHO in 2005. The original guidelines were designed for pyrethroid-treated nets and were based on the state of knowledge and LN technology at the time. Considerable experience in testing LNs has since been gained, and WHO published additional guidelines for monitoring the durability of LNs under operational conditions by 2013. No new guide line is released by WHO since 2013. WHO Pesticide Evaluation Scheme (WHOPES) gives full or interim recommendation LLINs that used for malaria control purposes. However, their performance needs to be monitored under various cultural and environmental settings to assess durability and long term effectiveness for malaria prevention and control. In view of the current wide scale distribution this protocol proposes to evaluate the wash resistance and efficacy of LLINs under laboratory and field conditions in Ethiopia.

The efficacy of the LLINs in killing mosquitoes and their wash resistance will be assessed using bioassay tests. The study will help to generate data on the efficacy of LLINs under local conditions which is important for the planning and implementation of the national malaria control programme. Therefore, in view of the current wide scale distribution, this study proposes to evaluate the wash resistance and efficacy of different brands of LLINs under field conditions in Ethiopia.

# 2. Purpose of the LLINs Protocol

The main purpose of this protocol is to assist national vector-borne disease control programme, and other relevant agencies, in monitoring the durability of LLINs under operational conditions. The information will be useful in planning the replacement of worn-out nets in LLINs programme, making decisions to procure the most suitable LLINs for the setting and understanding the factors associated with the durability of LLINs products. The principles and methods outlined in this document can, however, contribute to such evaluations.

This protocol is designed for monitoring various LLINs products. ALLINs is a factory treated mosquito net that is expected to retain its biological activity for a minimum number of standard washes as defined by WHO and a minimum time under field conditions. Currently, a LLINs is expected to retain its biological activity for at least 20 standards WHO washes under laboratory conditions and 3 years of recommended use under field conditions, as defined in the WHO guidelines. In addition, the methods described here can be used in monitoring the performance of LLINs. The protocol provides guidance and to serve as a basis for conducting LLINs. The protocol is intended for use by those responsible for malaria control. These include national malaria control programme personnel; regional malaria control programme, health facilities, government sectors other than the health sector, Non-Governmental Organizations (NGO), and relevant international and bilateral agencies and other donors in support of malaria vector control.

MIS 2015 presents findings on ownership of LLINs in malarious areas >2000m and ≤2500m above sea level(asl) shows that 64 percent of all households owned at least one LLIN in malarious areas (areas <2000m asl). On average, households in malarious areas own 1.18 LLINs per household.

Ethiopian vector control programme is to maintain universal coverage with LLINs and/or IRS in targeted areas. Based on new Malaria NSP (2014-2020) stratification and targeting of interventions, LLIN and IRS are being implemented together in high transmission stratum to bring down the malaria burden. The vector control programme should build or strengthen their capacity to monitor and evaluate the durability of LLINs distributed to targeted populations as a routine programme management activity. This should include measurement of three essential outcomes, namely survivorship or attrition rate, fabric integrity and insecticidal activity of LLINs over time under field conditions in the country.

# **3.LLINs Protocol Objectives**

# 3.1 General Objective

The main objective of this protocol is to provide current information and guide on assessing and evaluating LLINs registration by the Ministry of Animals and Natural Resources and procurement by the National Malaria Control Program/Federal Ministry of Health of Ethiopia that ultimately help in malaria prevention, control and elimination.

## 3.2 Specific objectives:

The specific objectives of this protocol is to:

- ✓ Determine the bio-efficacy of LLINs against *Anopheles arabiensis*, principal malaria vector insecticidal activity
- ✓ Evaluate wash resistance of LLINs through repeated community wash in the field setting
- ✓ Test the survivorship and fabric integrity of LLINs in various environments and cultural settings
- ✓ Evaluate the insecticide content at the beginning and over time as they are routinely used by people in various settings
- ✓ Determine the acceptability of LLINs by the community

# 4.Approach

Include a WHO position paper or protocol on which our protocol mainly relied on. If there is a need we could include other references here. Here where we should reflect our protocol mainly uses WHO guideline. Two main approaches can be used to study LLINs durability: (i) prospective longitudinal studies in which nets are followed from the time of distribution until a defined endpoint is reached; and (ii) retrospective, cross-sectional surveys to assess previously distributed nets in a representative sample of households. This protocol proposes to use prospective longitudinal monitoring.

# 4.1 Study site

The study can be conducted in all representative malarious areas of Ethiopia. The study site will be selected based on conditions of the location that may affect bed net usage, accessibility and local support and on-ground capacity. The sites should represent the environments and cultural settings in which LLINs can be distributed. The study site should be large enough to allow selection of sufficient numbers of nets during follow-up.

## 4.2 Sample size and net allocation

In order to estimate the number of LLINs for the study, the sample size necessary for a given degree of precision or to detect differences in durability between products should be calculated separately for each main outcome variable (e.g. Attrition rate, physical integrity). The sample size depends on the type of sampling: LLINs that are collected and taken away (after replacements are given) for bioassay and chemical residue analysis are lost to follow-up; therefore, the pool of nets at the start must be accordingly larger in order to have the same number of LLINs available for assessment of the core outcome variables; if nets are left in place after each assessment, the number needed will be smaller. The sample size should also be adjusted for the effect of a cluster design (between-cluster variation) of net assessment and for the expected attrition. If possible, the net products to be studied should be distributed in a fairly large population, in numbers that needed on the basis of the initial sample size calculation.

A subset of households will be selected from these for the follow-up study. Initial distribution to a large population and the selection of a sample at each follow-up should help to ensure that the results are representative and free of covert attempts to influence the attitudes or behaviour of the selected households. In studies in which more than one LLINs product is to be monitored, the different products can be allocated either to households or to individuals or sleeping places. When randomization is at household level, each household should be randomly assigned to receive one type of LLINs.

The number of LLINs that each household receives should be based on the national policy for universal coverage. Equal numbers of households should be assigned to receive each LLINs product to be monitored, although slightly different numbers of each product may distribute because of differences in the numbers of nets required for households in each treatment arm. Random allocation may be possible if a census is conducted well in advance and a master list of eligible households has been drawn up. Pre-printed lists with each household and LLINs product they are to receive should be provided at the time of distribution. If a list of households is not available at the time of distribution, LLINs products can be allocated to consecutive households in a systematic fashion, alternating the different products and providing sufficient nets to each household to cover all family members. Alternatively, different LLINs could be randomly assigned within the same household. This allows direct comparisons of net durability and preference and equal exposure of nets in different types of households (e.g. Rich and poor).

## 4.3 Sampling

If sampling is done at a net level, a list of randomly selected nets with their unique code numbers and information on the household to which they distributed (e.g. Household identification, name of head of household, Global Positioning System (GPS)should be given to the staff who are sampling the nets in the field, who should sample all the nets on the list. If sampling is one at the household level, the number of nets distributed to each household should be estimated, and then the number of households required to reach the estimated sample size should be determined. Sampling should be simple random sampling, so that there is an equal probability of selection of each household in the list. Determination of the sample size should take into account the precision and the difference necessary to detect each outcome measure for the different LLINs products.

The estimated sample size should also take into account variations between nets and between households. It should be based on the outcome that requires the largest sample, although subsamples can be taken for some measures (e.g. bioefficacy). The sample net should be labelled by the study organizers or the manufacturer, allowing easy reading of stored information (product, batch, manufacturing data, distribution date), as long as it has not faded or the label has been lost. Sample size on the basis of attrition, for outcomes such as bioefficacy, it may not be feasible to test large numbers of nets. If sampling is done at the household level and all nets in the household are sampled, the sample size should be adjusted for design effect and the questionnaire adjusted accordingly.

A sample of 250 LLINs per product will allow detection of a 10% point difference in LLINs attrition rate if the best-performing product has an attrition rate of 10%. This sample size will also allow detection of a 12% point difference in LLINs attrition rate if the best-performing product has an attrition rate of 20%. A list of additional households should be generated from the master list as alternatives for refusals and the absence of a person to interview. The number of nets available for monitoring fabric integrity will decrease over time; however, as observed in previous studies, the fabric integrity of surviving nets is not expected

to change much after a certain time if torn nets are thrown away (and hence lost to follow-up). With an attrition rate of 40% after 2 years, a sample of 250 LLINs per product will provide at least 150 nets for fabric integrity measurement, which is considered sufficient to detect major differences between products in a given setting. A subsample of nets that have been assessed for fabric integrity should be randomly selected and withdrawn (after replacement) for measuring insecticidal activity. In previous studies, 30 nets per LLINs product at each time were found sufficient for bio-efficacy testing, but a larger sample will provide more precision. As mentioned above, the overall number of nets needed for the study should be increased by the number withdrawn. Ideally, nets for bio-efficacy testing should be selected randomly from a roster of nets in the study. All registered products of LLINs by regulatory bodies will be included in the study.

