### 4.5 Attrition

Attrition is the proportion of nets no longer in use as intended after a defined period after their distribution to the households. Attrition can be categorized by the main reasons why a net is no longer used, namely decay (e.g. Destroyed, so torn and worn out that it is considered useless for protection against mosquitoes), absence (e.g. Stolen, given away, moved) or used for other purposes.

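### Section 4.3 allows alternate households for refusals and absences without limiting this to enrolment, so nets of unknown status can drop out of the attrition estimate, which may then be too low

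*Protocol*

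**What the plan says.** Protocol 4.3 (Sampling) provides for substitutes: "A list of additional households should be generated from the master list as alternatives for refusals and the absence of a person to interview". The sentence comes straight after the statement on detectable attrition differences with 250 nets per product. It names no stage of the study.

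Four other places bear on how it will be applied:

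- **4.2 (Sample size and net allocation):** "Initial distribution to a large population and the selection of a sample at each follow-up should help to ensure that the results are representative". Sampling is thus described as happening in each round, among households already holding nets. The same section has the study code of each net entered on the master list.
- **4.5 (Attrition):** "Attrition is the proportion of nets no longer in use as intended after a defined period after their distribution to the households". One category of loss is "absence (e.g. Stolen, given away, moved) or used for other purposes".
- **4.6 (Survivorship):** the proportion is taken over distributed nets, in the households that received them.
- **4.3, net-level option:** field staff receive a list of net codes and are the people "who should sample all the nets on the list". No alternates are mentioned for that option.

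The protocol gives no revisit rule, no count of substitutions by product, and no rule for the nets of a replaced household.

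**The concern.** Attrition is a proportion of nets handed out. If a sampled household cannot be interviewed and another takes its place, its nets leave both numerator and denominator without anyone learning what became of them. The sample is then conditioned on someone being present and willing. That may be related to the outcome, because a household that is absent or has left is one place where nets that were moved or given away would be found. The sample also looks complete afterwards, so the reader of the report gets no warning.

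Section 2 lists survivorship or attrition among three essential outcomes, and says the information is meant for replacement planning and procurement. An attrition figure that is too low would make nets appear to last longer than they do. If households with one product were unreachable more often than households with another, the comparison between products could be distorted too.

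**Working it through.** **1. Timing.** The sentence in 4.3 does not say that it applies at follow-up. Two readings are possible.

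- *Enrolment:* 4.2 describes a master list of eligible households drawn up from a census before distribution, and 4.4 gives nets to all households in the sample. Alternates would then fill places before nets are handed out.
- *Follow-up:* 4.2 selects a sample in each round, and 4.3 concerns nets already distributed. The Annex 1 interview, which 5.1.1 completes at each visit, asks about length of use, washing and holes.

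The second reading is well supported, but it is inferred. As written, field staff may substitute in any round.

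**2. The plan's own figure.** Section 4.3 says 250 nets per product detect 10% v 20% attrition, and 20% v 32%. It states no alpha or power. Assuming a two-sided 5% test of two proportions with no design effect:

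| Comparison | Power with 250 per product | n per product for 80% power |
|---|---|---|
| 10% v 20% | 88.2% | 199 |
| 20% v 32% | 86.6% | 209 |

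The detection statement is credible at above 80% power, although 250 itself cannot be reproduced without the missing inputs. It serves here only as the yardstick: a 10-point difference matters to this study.

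**3. Bounds on true attrition.** Let *a* be attrition among reached nets (replacements assumed to behave like them), *m* the share of sampled nets substituted, and *b* attrition among the replaced nets.

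True attrition = (1 − m)·a + m·b

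The substituted sample reports *a*. The documents give neither *m* nor *b*, so *m* is varied and *b* runs from 0 to 1:

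| m | Observed 10% | Observed 20% | Observed 40% |
|---|---|---|---|
| 5% | 9.5% to 14.5% | 19% to 24% | 38% to 43% |
| 10% | 9% to 19% | 18% to 28% | 36% to 46% |
| 20% | 8% to 28% | 16% to 36% | 32% to 52% |

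For m = 10% and a = 10%, the lower bound is 0.90 × 10 = 9% and the upper bound is 9 + 10 = 19%. The width always equals *m*, whatever the sample size.

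**4. A milder assumption.** If unreached nets are lost twice as often as reached ones and m = 10%, an observed 10% means a true 0.90 × 10 + 0.10 × 20 = 11%. Observed 10%, 20% and 40% are then too low by 1, 2 and 4 points. If b = a the bias is zero, and if b < a it is upward.

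**5. Effect on the comparison.** Take true rates of 10% v 20%, with the same substitution share and the same doubling of loss in both products. The observed rate is the true rate divided by (1 − m) + 2m:

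- m = 10%: 10/1.1 = 9.1% v 20/1.1 = 18.2%, power 84%
- m = 20%: 10/1.2 = 8.3% v 20/1.2 = 16.7%, power 81%

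The ranking is kept, the difference shrinks a little, and power falls from 88%.

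**The case against.** The strongest reply is that the sentence may concern enrolment only. The census-based list in 4.2 and the distribution rule in 4.4 fit that reading, and then no outcome data are lost. This stands as a limit on confidence. It does not remove the point, because nothing in the text confines the rule to enrolment.

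Second, the categories in 4.5 describe what happened to a net, not to a household. A net that left with its owners may still be in use, and someone who is out on the day of the visit need not have lost a net. This stands. It rules out treating every household that has moved as attrition.

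Third, a reader might infer that attrition is certainly understated, and by a lot. With 5% to 15% of households unreachable and 50% to 100% of their nets lost, an observed 10% would hide a true 12.0% (0.95 × 10 + 0.05 × 50) to 23.5% (0.85 × 10 + 0.15 × 100). With all unreached nets lost, and 5% substituted for one product against 15% for another, 14.5% v 23.5% would be reported as 10% v 10%. The documents support none of these inputs, so the figures illustrate what is possible and do not estimate the bias.

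Fourth, a reader might see a contradiction with the longitudinal design in section 4, where "nets are followed from the time of distribution until a defined endpoint is reached", or with the net-level rule in 4.3. Both are weak. Section 4.2 allows a fresh sample each round, and 4.3 offers net-level and household-level sampling as alternative modes, which may have different field rules.

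Finally, the treatment of unknown status can be left to an analysis plan, and the product criteria in 5.3.1 and 5.3.2 rest on bioassays, not attrition. The second part lowers the severity. The first part does not help: if a replaced household is not recorded, no later analysis can recover it.

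**Conclusion.** The concern holds in a limited form. Section 4.3 permits alternates without restricting them to enrolment. Together with the sampling in each round described in 4.2, this allows sampled nets of unknown status to drop out of outcomes that 4.5 and 4.6 define on distributed nets. Attrition can be understated. That is the likely direction because absence and net loss may go together, but it is not certain.

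The documents do not fix the size. With 10% of sampled nets substituted (assumed), an observed 10% is compatible with 9% to 19%, a range as wide as the 10-point difference named in 4.3. The bias vanishes if unreached nets fare the same as reached ones. If substitution is about equally frequent and equally selective across products, levels shift more than ranking. Severity is moderate, with medium confidence because the timing is inferred.

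**What to change.** Amend the paragraph in 4.3:

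- Limit alternates to households that refuse before nets are handed out.
- Do not substitute at follow-up. If spare capacity is wanted, draw a larger sample at the start of the round and visit all of it.
- Keep every sampled household and net code in the denominator.
- Record, by product, how many were not reached and why.
- Classify a net as attrition by absence only when its own status has been established under 4.5. Code the rest as status unknown.
- Report attrition by product twice: with all unknowns counted as lost, and with all counted as surviving. These bounds need no earlier visit, so they work even when a fresh sample is drawn each round.

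The cost is one protocol paragraph and one status code on the field list. The downside is somewhat fewer completed interviews per round, and an attrition figure that is wider and possibly less favourable.

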#### 5.3.2 For case II

The same *Anopheline* species and same procedure implemented in all cases regarding cone bioassay, following the regeneration of the insecticide or bioavailability given by the manufacturer. The bioassay will be carried on randomly selected 30 sample nets from each type every six months. At the end of three years, at least 80% of nets meet the cut off criteria for either the WHO cone bioassay test or the tunnel test, and then the product meets the definition for a LLINs.

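### Adding one net at the start for each surviving net withdrawn does not by itself keep the number of nets for fabric integrity at the last Case II round or two

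*Protocol*

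**What the plan says.** Section 4.2 explains that nets removed for bioassay and residue analysis are lost to follow-up, so "the pool of nets at the start must be accordingly larger in order to have the same number of LLINs available for assessment". The same section also asks for the sample size to be adjusted for clustering and for expected attrition. It gives no formula for either.

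Section 4.3 sets the base number through attrition: "A sample of 250 LLINs per product will allow detection of a 10% point difference in LLINs attrition rate" when the best product loses 10%, and 12 points when it loses 20%. For fabric integrity it says: "With an attrition rate of 40% after 2 years, a sample of 250 LLINs per product will provide at least 150 nets". It then describes the withdrawals: "A subsample of nets that have been assessed for fabric integrity should be randomly selected and withdrawn", and "30 nets per LLINs product at each time were found sufficient for bio-efficacy testing". Referring back to section 4.2, it ends with the rule that "the overall number of nets needed for the study should be increased by the number withdrawn". No enlarged total is given.

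Section 5.1.2 has Case II, including fabric integrity, studied every six months for three years. Section 5.3.2 sets the bioassay sample: "The bioassay will be carried on randomly selected 30 sample nets from each type every six months".

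**The concern.** The withdrawn nets are drawn from nets that have just been assessed, so each has survived to that round. If a share S(t) of nets survives to time t, one survivor at t corresponds to 1/S(t) nets at distribution. An extra net handed out at the start has only probability S(t) of still being there at t. Adding one net at the start per net withdrawn later therefore replaces less than was taken, whatever the shape of the loss curve, as long as some loss comes before the withdrawal.

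The deficit builds up over rounds and is largest at the end of Case II. At stake is the precision of late fabric-integrity comparisons between products. Products with high attrition lose most.

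**Working it through.** **Inputs.** From section 4.3: 250 nets per product, 40% attrition at 2 years, and 30 nets per product withdrawn at each time after assessment. From sections 5.1.2 and 5.3.2: rounds every six months for three years. Assumed here, because the protocol does not give them: a constant loss rate continued to month 36, so S(t) = 0.6^(t/24), and all 30 nets withdrawn at every round.

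**The protocol's own figure.** 250 × 0.60 = 150 nets at month 24. This reproduces, with no withdrawals counted.

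**Formula.** With W nets added at the start, the number left for assessment at round T is

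left(T) = (250 + W) × S(T) − 30 × S(T) × Σ 1/S(t), summed over rounds t before T.

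The number without withdrawals is 250 × S(T). The two are equal when W = 30 × Σ 1/S(t).

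| Month | 6 | 12 | 18 | 24 | 30 | 36 |
|---|---|---|---|---|---|---|
| S(t) | 0.880 | 0.775 | 0.682 | 0.600 | 0.528 | 0.465 |
| 30/S(t) | 34.1 | 38.7 | 44.0 | 50.0 | 56.8 | – |

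Addition needed for month 36: 34.1 + 38.7 + 44.0 + 50.0 + 56.8 = 223.6, a start of about 474 per product. The one-for-one rule gives 5 × 30 = 150 (start 400) if only withdrawals before month 36 count, or 6 × 30 = 180 (start 430) if the month-36 draw counts as well.

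| Round | Without withdrawals | 150 added | 180 added |
|---|---|---|---|
| 24 | 150 | 170 | 188 |
| 30 | 132 | 123 | 139 |
| 36 | 116 | 82 | 96 |

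At month 36, for example: 430 × 0.4648 − 0.4648 × 223.6 = 199.9 − 103.9 = 95.9.

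**Precision of a mean over surviving nets at month 36.** √(116.2/95.9) = 1.10 and √(116.2/82.0) = 1.19, so standard errors are 10% to 19% larger.

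**Other curves through 60% at month 24** (linear, and Weibull with shape 1.5 and 2, together with the constant rate). The month-36 shortfall is 13 to 20 nets with 180 added and 23 to 34 with 150 added. The start needed is about 471 to 474.

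**Other attrition levels** (constant rate, 180 added, month 36). At 20% two-year attrition, 180 nets against 179, so no shortfall. At 30%, 136 against 146. At 50%, 60 against 88.

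**Attrition itself.** A net withdrawn at month t is known to have survived to t, so it still counts in a life-table estimate. The Greenwood standard error for month-36 survival in the 40% scenario is 0.0315 for 250 nets without withdrawals, which equals √(0.4648 × 0.5352/250). With 30 withdrawn at each of months 6 to 30, it is 0.0310 for a start of 400 and 0.0292 for 430.

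**The case against.** The strongest reply is that section 4.2 already asks for an adjustment for expected attrition, and the rule in section 4.3 refers back to it. A pool sized by both instructions need not fall short: on the same assumptions, (116 + 150)/0.465 gives about 573 nets, more than the 474 needed. This stands to the extent that one-for-one addition is not the only allowance the protocol asks for. It does not rescue the rule. The worked example in section 4.3 lets 250 fall to 150 through attrition, and the section then adds the withdrawn number without inflating it. Nothing says that the attrition adjustment applies to the withdrawn nets. Depending on the reading, the start is 400, 430 or 573.

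Second, the only count that the protocol states is 150 at month 24, and no enlarged total is printed, so no printed figure is wrong. That is correct. The month-24 count is met with 120 added (152), 150 (170) or 180 (188). It fails (134) only if just the 90 nets withdrawn before that visit are added, an unlikely way to size a three-year study.

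Third, section 4.2 prefers wide distribution with a sample selected at each follow-up. Where the pool is large, counts can be made up from it. The shortfall concerns a pool sized by the rule itself. Section 4.3 also expects the fabric integrity of surviving nets to change little after a certain time, which softens the consequence.

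A reader might further infer that attrition estimates or the three-year judgement of the product are weakened. The documents do not support that. The 250 nets are justified by attrition, whose life-table precision is no worse than planned in the 40% scenario. The verdict in section 5.3.2 rests on 30 bioassayed nets per type, and 82 to 96 remain to draw them from.

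**Conclusion.** The point holds in a limited form. The rule in section 4.3 does not by itself deliver the same-number aim of section 4.2, and the attrition adjustment in section 4.2 is not tied to the withdrawn nets.

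The loss is confined to the precision of fabric integrity late in Case II. At 40% two-year attrition, month 36 is short by about 20 nets of 116 (180 added) or 34 (150 added). Month 30 is short only if 150 are added. It would be too broad to say that later rounds in general are under-supplied, and at 20% two-year attrition with 180 added there is no shortfall at all.

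The direction follows from withdrawing survivors. The size rests on the assumed loss curve, its continuation past two years, and withdrawal of all 30 nets at every round. This is a sizing rule to be reworded; it does not invalidate the design.

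**What to change.** Reword the rule in section 4.3 so that the starting number is increased by the sum, over rounds, of the nets withdrawn divided by the expected proportion surviving at that round. Equivalently, say that the attrition adjustment in section 4.2 applies to the withdrawn nets too, at the survival expected when each is taken. State the resulting total per product. In the scenario above this is about 474, which is 44 more than 430 or 74 more than 400. It should be settled before distribution, because nets added later would not share the same follow-up time.

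If no more nets can be supplied, keep the one-for-one addition, drop the same-number aim for the last round or two, and state the number of nets expected for fabric integrity at each round. With 180 added that would be about 188, 139 and 96 at months 24, 30 and 36. This costs only the wording.
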